7.1.1.3.2. Drug Restart Following Transient Resolving Liver Events Not Related to Study intervention

Restart refers to resuming study treatment following liver stopping events in which there is a clear underlying cause (other than DILI) of the liver event (e.g. biliary obstruction, pancreatic events, hypotension, acute viral hepatitis). Furthermore, there should be no evidence of alcoholic hepatitis or hypersensitivity, and the study treatment should not be associated with HLA markers of liver injury.

Approval by the VSLC for drug restart can be considered where:

- Investigator requests consideration for study treatment restart if Liver chemistries have a clear underlying cause (e.g., biliary obstruction, hypotension and liver chemistries have improved to normal or are within 1.5 x baseline and ALT <5xULN).
- Furthermore, there should be no evidence of fever, rash, eosinophilia, hypersensitivity, alcoholic hepatitis or possible study treatment-induced liver, and the drug should not be associated with HLA markers of liver injury. (If restart of TRIUMEQ or any other abacavir- containing product is being considered then the Subject must be HLA-B*5701 negative).
- Ethics Committee or Institutional Review Board approval of drug restart/rechallenge must be obtained, as required.
- If restart of drug is approved by the VSLC in writing, the subject must be provided with a clear description of the possible benefits and risks of drug administration, including the possibility of recurrent, more severe liver injury or death.
- The subject must also provide signed informed consent specifically for the restart. Documentation of informed consent must be recorded in the study chart.
- Study drug must be administered at the dose specified by the VSLC.
- Subjects approved by the VSLC for restarting IP must return to the clinic once a week for liver chemistry tests for a minimum of one month and thereafter for as

long as clinically indicated and then laboratory monitoring may resume as per protocol.

- If after study treatment re-start, subject meets protocol-defined liver chemistry stopping criteria, follow usual stopping criteria instructions..
- The Medical Monitor and the Ethics Committee or Institutional Review Board as required, must be informed of the subject's outcome following study treatment restart
- Any adverse events should be recorded on the appropriate eCRF(s), and reported where applicable, as per Section 8.5.

7.1.2. QTc Stopping Criteria

A participant who has a QTc interval >550 msec considered causally related to IP will be withdrawn from the study. The QTc should be based on averaged QTc values of triplicate electrocardiograms obtained over a brief (e.g., 5 to 10 minute) recording period.

If an alternative cause of the QT prolongation is determined (e.g., participant receiving drug known to cause prolonged QT or TdP), the IP may be restarted (or continued) after consultation and agreement with the Medical Monitor. RPV and RPV LA should not be administered to participants who are receiving a drug known to be associated with TdP.

When performing ECGs, the *same* QT correction formula *must* be used for *each individual participant* to determine eligibility for, and discontinuation from, the study. This formula may not be changed or substituted once the participant has been enrolled.

For example, if a participant is eligible for the protocol based on QTcB, then QTcB must be used for discontinuation of this individual participant as well.

Once the QT correction formula has been chosen for a participant's eligibility, the *same formula* must continue to be used for that participant *for all QTc data being collected for data analysis*. Safety ECGs and other non-protocol specified ECGs are an exception.

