RPV: Corrected QT interval (QTc) prolongation	In healthy subjects, supratherapeutic doses of RPV (75 mg once daily and 300 mg once daily) have been shown to prolong the QTc interval of the electrocardiogram (ECG). RPV at the recommended dose of 25 mg administered once daily is not associated with a clinically relevant effect on QTc.	Subjects who use medications which are associated with Torsades de Pointes are excluded. Day 1 ECG to identify those with pre-existing prolonged QT interval. Per sentinel event management, study drug will be discontinued when a prolonged QT is identified.
RPV: Fat Redistribution	Redistribution/accumulation of body fat, including central obesity, dorsocervical fat enlargement (buffalo hump), peripheral wasting, facial wasting, breast enlargement, and “cushingoid appearance” have been observed in patients receiving ART. The mechanism and long-term consequences of these events are currently unknown. A causal relationship has not been established.	Routine monitoring of adverse reactions will be performed.

- a. Careful monitoring of events will be conducted using serious adverse event (SAE) reports and alerts for Grade 3/4 laboratory toxicities (per Division of Acquired Immune Deficiency Syndrome [AIDS] toxicity gradings for HIV-infected patients). Serious/severe events will be managed appropriately including, but not limited to, withdrawal of study drug, and will be followed to resolution as per Sponsor’s standard medical monitoring practices. Clinical Safety Data will be routinely reviewed in GlaxoSmithKline (GSK) Safety Review Team meetings. This will include in-stream review of data from this clinical trial on a routine basis, review of aggregate data on a protocol and program basis when available, and review of competitor data from the literature.

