
Concomitant Medications
 
24. Exposure to an experimental drug (with the exception of those in the LATTE study including CAB and RPV) or experimental vaccine within either 30 days, 5 half-lives of the test agent, or twice the duration of the biological effect of the test agent, whichever is longer, prior to Day 1 of this study;
 
25. Treatment with any of the following agents within 28 days of Day 1:

- radiation therapy;
 - cytotoxic chemotherapeutic agents;
 - tuberculosis therapy with the exception of isoniazid (isonicotinylhydrazid [INH]);
 - anti-coagulation agents;
 - Immunomodulators that alter immune responses such as chronic systemic corticosteroids, interleukins, or interferons. Note: Participants using short-term (e.g. ≤ 21 days) systemic corticosteroid treatment; topical, inhaled and intranasal corticosteroids are eligible for enrolment.
26. Use of medications which are associated with Torsade de Pointes must be discussed with the Medical Monitor to determine eligibility. (See SPM for a list of relevant medications)
27. Participants receiving any prohibited medication and who are unwilling or unable to switch to an alternate medication. Note: Any prohibited medications that decrease CAB, RPV and/or DTG concentrations should be discontinued for a minimum of four weeks or a minimum of three half-lives (whichever is longer) prior to the first dose and any other prohibited medications should be discontinued for a minimum of two weeks or a minimum of three half-lives (whichever is longer) prior to the first dose

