Drugs with a known risk of Torsade des Pointes (TdP) should be used with caution when on rilpivirine (see SPM for list of drugs associated with TdP).

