8.7.8. QTc Prolongation

Participants with an average QTc interval > 550 msec from three or more tracings separated by at least 5 minutes should have IP discontinued. These criteria are based on an average QTc value of triplicate ECGs. If an ECG demonstrates a prolonged QT interval, obtain 2 more ECGs over a brief period (~ 5 -10 minutes) and use the averaged QTc values of the 3 ECGs to determine whether the participant should be discontinued from the study. If an alternative cause of the QT prolongation is determined (e.g., participant receiving drug known to cause prolonged QT or TdP), then IP may be restarted after consultation with, and agreement by, the Medical Monitor.

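### The protocol contradicts itself on rilpivirine with drugs associated with Torsade de Pointes: one section permits the combination with caution, another bars it, and the entry wording also conflicts

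*Protocol*

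**What the plan says.** Five places in the protocol deal with drugs associated with TdP.

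- **Section 2.3.1, DTG + RPV risk table, RPV row on QTc prolongation:** "Subjects who use medications which are associated with Torsades de Pointes are excluded".
- **Section 5.2, exclusion criterion 26:** "Use of medications which are associated with Torsade de Pointes must be discussed with the Medical Monitor to determine eligibility".
- **Section 6.11.1, permitted medications:** "Drugs with a known risk of Torsade des Pointes (TdP) should be used with caution when on rilpivirine".
- **Section 7.1.2, QTc stopping criteria:** where an alternative cause of the prolongation is found, the example given being a drug known to prolong QT or cause TdP, "the IP may be restarted (or continued) after consultation and agreement with the Medical Monitor". The next sentence reads: "RPV and RPV LA should not be administered to participants who are receiving a drug known to be associated with TdP".
- **Section 8.7.8, QTc prolongation:** for the same situation, "then IP may be restarted after consultation with, and agreement by, the Medical Monitor". The bar on rilpivirine is not repeated.

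Section 6.11 leaves concomitant medication to the investigator's discretion, apart from what Section 6.11.2 prohibits. The lists in Section 6.11.2 and its subsections contain no TdP category.

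**The concern.** A site meets this question at three moments: when it checks eligibility, when someone prescribes a new drug during the study, and when an ECG shows a long QTc. At each one, the answer depends on which section the site opens.

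The co-medication rule matters because ECGs are sparse. After Day 1 they are scheduled only at Month 12 and at withdrawal, and a note in Section 7 says they are not routinely conducted. QT prolongation is also a listed adverse event of special interest for RPV in SAP Section 8.3. SAP Section 4.1 summarises important deviations in patient management, and whether rilpivirine given alongside a TdP drug counts as one depends on whether Section 6.11.1 or Section 7.1.2 is taken as the rule.

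**Working it through.** No arithmetic applies. The check sorts the statements by the stage they govern and compares them within each stage.

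| Stage | First statement | Second statement | Compatible? |
|---|---|---|---|
| Entry | 2.3.1 (DTG + RPV table): excluded, no discretion stated | 5.2, criterion 26: decided after discussion with the Medical Monitor | No, for those electing DTG + RPV |
| On treatment | 6.11.1: permitted, with caution | 7.1.2: no RPV or RPV LA | No, in either arm |
| After QT prolongation with a TdP drug as the cause | 7.1.2, first sentence, and 8.7.8: restart possible with Medical Monitor agreement (7.1.2 adds continuation) | 7.1.2, next sentence: no RPV or RPV LA while receiving the drug | Unclear |

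**Do the sections mean the same drugs?** The wording varies slightly between known risk and known association. Section 6.11.1 itself points to the Study Procedures Manual (SPM) for its list of drugs associated with TdP, so it treats the two as one class. Criterion 26 also cites the SPM for the relevant medications. In both places the SPM supplies drug names, not the action to take.

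**Entry.** Take a participant who elects DTG + RPV and uses such a drug on Day 1. Under Section 2.3.1 the participant is out. Under criterion 26 the participant may be in. For a participant electing CAB LA + RPV LA, the RPV LA risk table carries no matching exclusion sentence, so criterion 26 stands alone at entry.

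**On treatment.** Take a participant in either arm who is prescribed such a drug mid-study. Section 6.11.1 allows it with caution. Section 6.11.2, where a site would look for a ban, is silent. Section 7.1.2 says the rilpivirine component should not be given. Both regimens contain rilpivirine, so the same co-prescription is allowed by one section and ruled out by another.

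**After a QTc event.** Section 7.1 uses IP to cover either formulation of CAB or RPV and also DTG + RPV, so permission to restart or continue IP includes rilpivirine. Restarting can be squared with the bar if the TdP drug has been stopped first. Continuing is harder to square, because the example is a participant who is receiving the drug.

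**What is consistent.** The 550 msec figure is the same in Sections 7, 7.1.2 and 8.7.8. Criterion 20 sets the entry QTc limit at 450 msec, or 480 msec with bundle branch block. Section 7.1.2 requires one correction formula per participant.

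**The case against.** Several counter-arguments have force.

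- **The statements do not all compete.** Two govern entry and two govern treatment. This stands: the defect is one contradiction per stage, not four rival rules for one decision.
- **Section 5.2 governs eligibility.** Section 2.3.1 only summarises risk mitigation, and a site checking eligibility works from criterion 26. That makes the entry mismatch less likely to mislead, but the two sentences still disagree for DTG + RPV.
- **Section 7.1.2 can be read as coherent.** Its second sentence may limit the first: restart only once the TdP drug is gone. This is fair for restarting and leaves only the word *continued* unclear. A narrower reading, that the bar applies only after a QTc event, would ease the clash with Section 6.11.1, but the sentence states no such condition.
- **The Medical Monitor provides a common decision point.** This is true of criterion 26 and of restart in Sections 7.1.2 and 8.7.8. It is not true of the caution in Section 6.11.1 or the bar in Section 7.1.2.
- **Outside labels may settle it.** Sections 6.11.1 and 6.11.2.4 refer to prescribing information, which is not available here. Whatever it says, the protocol's own sentences would still disagree.

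A reader might also infer three stronger points that the documents do not support.

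- **That the whole QT safeguard fails.** The stopping threshold, the entry limit and the Day 1 ECGs are unaffected.
- **That ethics committees are misinformed.** They review the full protocol, including criterion 26 and Section 6.11.
- **That the conflict cannot be resolved by holding a dose because RPV LA persists.** Persistence means that co-exposure does not end promptly when injections stop. It does not make a conflict of wording unresolvable, and it has no bearing on the oral arm.

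**Conclusion.** The protocol is wrong as written on one defined matter, co-medication with TdP-associated drugs. The on-treatment contradiction between Sections 6.11.1 and 7.1.2 is plain and reaches both arms. The entry contradiction between Section 2.3.1 and criterion 26 is direct only for participants electing DTG + RPV. The permission to restart or continue in Section 7.1.2, together with the shorter text in Section 8.7.8, is unclear rather than flatly contradictory.

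The size cannot be put as a count. The documents give no frequency of TdP drug use among the approximately 100 planned participants. The effect falls on eligibility decisions, co-prescribing, handling of QTc events and the recording of deviations. It does not reach the sample size or the primary virologic estimate.

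The conclusion assumes that the sections refer to the same class of drugs, which the SPM reference in Section 6.11.1 supports, and that the bar in Section 7.1.2 is general, as it is worded.

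**What to change.** The sponsor should reconcile Sections 2.3.1, 5.2 (criterion 26), 6.11.1, 7.1.2 and 8.7.8 so that one entry rule and one on-study rule are stated in the same terms throughout. Section 6.11.2 should be aligned with the result. The text should also say explicitly what applies when a TdP drug is the alternative cause of QT prolongation, including whether restarting and continuing are treated alike. The two rules need to fit together, because a participant admitted under the first falls at once under the second. Which rule to adopt is a clinical decision for the sponsor, and none is proposed here.

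The cost is a protocol clarification. No analysis, sample size or data collection changes.

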7.1.3. Virologic Failure

Only plasma HIV-1 RNA values determined by the central laboratory will be used to assess virologic failure.

7.1.4. Definition of Protocol-Defined Confirmed Virologic Failure

For the purposes of clinical management in this study, CVF is defined as:

Rebound as indicated by two consecutive plasma HIV-1 RNA levels ≥ 200 c/mL after prior suppression to < 200 c/mL.

7.1.5. Managing Virologic Failure

Following study entry, no changes, or intensification of ART will be permitted prior to protocol-defined virologic failure, outside of the planned protocol regimens. Only plasma HIV-1 RNA values determined by the central laboratory will be used to assess virologic failure. Baseline plasma HIV-1 RNA is the assessment completed on study Day 1. The definition of confirmed virologic failure does not apply to participants in the LTFU Phase. These participants will be followed for the emergence of viral resistance.

Inadequate adherence is a common cause for virologic failure, and should be explored as a first step in the management of study participants (e.g., at the first indication of inadequate virologic response or rebound). Upon notification that a participant's HIV-1 RNA plasma level qualifies him/her as a suspected virologic failure (SVF), the Investigator should query the participant regarding intercurrent illness, recent immunization, or interruption of oral therapy.

7.1.5.1. HIV-1 RNA Blips

HIV-1 RNA “blips” are not usually associated with subsequent virologic failure [DHHS, 2016]. Although the implications of persistent HIV-1 RNA levels between the lower level of detection and <200 c/mL are unclear, the risk of emerging resistance is believed to be relatively low.

Participants with transient increases in HIV-1 RNA (‘blips’ HIV-1 RNA <200 c/mL) are not considered suspected virologic failures and do not require a change in therapy.

Participants who have a HIV-1 RNA ≥ 50 c/mL and <200 c/mL at the key analysis timepoints (Month 12 and End of study must return to the clinic as soon as possible (but no later than 4 weeks after the date of the Month 12 and End of study visit, respectively) for a repeat HIV-1 RNA test such that the result falls within the same analysis window.

In order to better characterize HIV-1 RNA ‘blips,’ if there is a known reason / explanation for the blip (e.g., immunization, allergies, etc), the study team should be notified of the reason and case context.

If the Investigator has concerns regarding persistent low level viremia (HIV-1 RNA ≥ 50 c/mL and <200 c/mL), the Medical Monitor should be contacted to discuss participant management. Following discussion with the Medical Monitor, additional viral load testing may be performed between visits to determine the appropriate participant disposition for the next scheduled visit

7.1.5.2. Suspected Virologic Failure

Upon notification that a participant's HIV-1 RNA plasma level meets the definition of virologic failure, the Investigator should confirm the definition is met by initiating a repeat of the HIV-1 RNA assessment.

The following guidelines should be followed for scheduling confirmatory HIV-1 RNA testing in an effort to avoid false-positive results:

- Confirmatory testing should be scheduled within 2 to 4 weeks following resolution of any intercurrent illness, during which time the participant should receive full dose of all study intervention.
- Confirmatory testing should be scheduled at least 4 weeks following any immunization, during which time the participant should receive full dose of all study intervention.
- If therapy is interrupted* due to toxicity management, non-compliance, or other reasons, confirmatory testing should be scheduled 2 to 4 weeks following resumption of full dose of all study intervention.
- The participant should have received full dose of study intervention for at least 2 weeks at the time confirmatory plasma HIV-1 RNA testing is done.

*Note: treatment interruption guidelines above may not apply for participants on CAB LA + RPV LA treatment. The study team should be contacted to discuss any treatment interruptions for participants meeting the definition of virologic failure.

In addition, the Investigator should query the participant regarding intercurrent illness, recent immunization, or interruption of therapy.

Sites should contact the Medical Monitor to discuss individual participants, whenever necessary.

7.1.5.3. Confirmed Virologic Failure

Participants with CVF must be discontinued from study intervention. However, participants who have received at least one dose of CAB LA or RPV LA prior to confirming virologic failure will remain in the study on oral HAART in the LTFU Phase.

A plasma sample from the suspected virologic failure visit as well as Day 1 (if baseline HIV-1 RNA level ≥ 200 c/mL) will be sent for genotypic and phenotypic resistance testing and the result made known to the Investigator when available. A plasma sample from the confirmation visit will be obtained for storage. This sample may be used for possible future analyses, e.g., for genotypic and phenotypic analyses of participants who experience virologic failure.

For all participants who meet CVF, baseline and suspected virologic failure plasma samples with HIV-1 RNA level ≥ 200 c/mL will be analyzed in an attempt to obtain genotype/phenotype data on as many samples as possible. Plasma samples for storage will also be obtained at unscheduled visits including confirmation of CVF. Participants may continue to receive study drug at the discretion of the investigator until results of resistance testing are available at which time the participant must be discontinued from the study. Even if genotype/phenotype data cannot be generated, participant must also be discontinued from the study intervention.

If a participant is prematurely discontinued from the study intervention, the investigator must make every effort to perform the Withdrawal Visit evaluations outlined in the Time and Events. These data will be recorded as they comprise essential evaluations needed to be done before discharging any participant from the study.

